2.8.1.1 Adverse events of clinical trial safety disclosure

For the legal requirements of ClinicalTrials.gov and EudraCT, two required tables of on-treatment/post-treatment adverse events which are not serious adverse events with an incidence

greater than 5% and on-treatment/post-treatment deaths, serious adverse events and SAEs suspected to be related to study treatment will be provided by system organ class and preferred term on the safety set population. Events that occurred during on-treatment period and those in post-treatment period (see definitions in [Section 2.1.1](#)) will be reported separately.

If for the same patient, several consecutive AEs (irrespective of study treatment causality, seriousness and severity) occurred with the same SOC and PT:

- a single occurrence will be counted if there is ≤ 1 day gap between the end date of the preceding AE and the start date of the consecutive AE
- more than one occurrence will be counted if there is > 1 day gap between the end date of the preceding AE and the start date of the consecutive AE

For occurrence, the presence of at least one SAE / SAE suspected to be related to study treatment / non SAE has to be checked in a block e.g., among AE's in a ≤ 1 day gap block, if at least one SAE is occurring, then one occurrence is calculated for that SAE.

2.8.1.2 Adverse events of special interest / grouping of AEs

An adverse event of special interest is a grouping of adverse events that are of scientific and medical concern specific to compound ruxolitinib. These groupings are defined using MedDRA terms, SMQs (standardized MedDRA queries), HGLTs (high level group terms), HLT (high level terms) and/or PTs (preferred terms). Customized SMQs (CMQs) may also be used. A CMQ is a customized group of search terms which defines a medical concept for which there is no official SMQ available or the available SMQ does not completely fit the need. It may include a combination of single terms and/or an existing SMQ, narrow or broad.

For each AESI, number and percentage of patients with at least one event of the AESI occurring during on-treatment period will be summarized. Summaries of AESIs will be provided by group (specifying grade, SAE, relationship, leading to treatment discontinuation, leading to dose adjustment/interruption, hospitalization, death etc.).

A listing of all grouping levels down to the MedDRA preferred terms used to define each AESI will be generated.

In addition to summarizing infections by CTCAE grade, they will also be summarized using infection severity (protocol Appendix 1) for the on-treatment period. A listing of infection with infection severity will be generated and the events with start date outside of on-treatment period will be flagged.

2.8.2 Deaths

Separate summaries for on-treatment and all deaths (including post-treatment death) will be produced by Age group, system organ class and preferred term.

All deaths will be listed, and deaths occurred outside of on-treatment period will be flagged. A separate listing of deaths prior to starting treatment will be provided for all screened patients.

2.8.3 Laboratory data

On analyzing laboratory, data from all sources (central and local laboratories) will be combined. The summaries will include all assessments available for the lab parameter collected no later than end of the on-treatment periods.

Grading of laboratory values will be assigned programmatically as per NCI Common Terminology Criteria for Adverse Events (CTCAE) version 4.03. The calculation of CTCAE grades will be based on the observed laboratory values only, clinical assessments will not be taken into account.

CTCAE Grade 0 will be assigned for all non-missing values not graded as 1 or higher.

For laboratory tests where grades are not defined by CTCAE v4.03, results will be categorized as low/normal/high based on laboratory normal ranges.

The following summaries will be produced for hematology and biochemistry laboratory data (by laboratory parameter and Age group):

- Shift tables using CTC grades to compare baseline to the worst on-treatment value
- For laboratory tests where CTC grades are not defined, shift tables using the low/normal/high/(low and high) classification to compare baseline to the worst on-treatment value.

The following listings will be produced for the laboratory data:

- Listings of all laboratory data, with CTC grades and classification relative to the laboratory normal range. Lab data collected during the post-treatment period will be flagged.
- Listing of all CTC grade 3 or 4 laboratory toxicities

In addition to the above mentioned tables and listings, other exploratory analyses, for example figures plotting time course of raw or change in laboratory tests over time or box plots may be produced.

2.8.4 Other safety data

2.8.4.1 ECG and cardiac imaging data

Not applicable.

2.8.4.2 Vital signs

Vital sign assessments are performed in order to characterize basic body function. The following parameters were collected: height or body length (cm), weight (kg), body temperature (°C), pulse (beats per minute), systolic and diastolic blood pressure (mmHg). The body surface area (BSA in m²) and body mass index (BMI in kg/m²) are derived using the following formulas:

BSA: (Height (cm) x Weight (kg) / 3600)^{0.5}

BMI: Weight (kg) / Height² (m²)

Data handling

Vital signs collected on treatment will be summarized. Values measured outside of on treatment period will be flagged in the listings.

Clinically notable vital sign criteria for blood pressure or weight (see below) are based on the height of the subject. Since height might not be measured at each visit, the last available height value before that assessment date will be used instead, i.e. using LOCF as imputation method.

Data analysis

For analysis of vital signs the clinically notable vital sign criteria depending on the patient's age are provided in [Table 2-4](#) below. Criteria should be applied according to the age at vital sign assessment rather than age at baseline.

Table 2-4 Criteria for notably abnormal vital signs

Vital sign (unit)	Clinically notable criteria			
	High			Low
Systolic blood pressure [mmHg]	≥ 95th percentile of the age and height group ¹			≤ 5th percentile of the age and height group ¹
Diastolic blood pressure [mmHg]	≥ 95th percentile of the age and height group ¹			≤ 5th percentile of the age and height group ¹
Body temperature [°C]	≥ 38.4°C			≤ 35.0°C
Pulse rate [bpm] ²	12-<18 months	> 140	12-<18 months	< 103
	18-<24 months	> 135	18-<24 months	< 98
	2-<3 years	> 128	2-<3 years	< 92
	3-<4 years	> 123	3-<4 years	< 86
	4-<6 years	> 117	4-<6 years	< 81
	6-<8 years	> 111	6-<8 years	< 74
	8-<12 years	> 103	8-<12 years	< 67
	12-<15 years	> 96	12-<15 years	< 62
	≥ 15 years	> 92	≥ 15 years	< 58
Weight ³	increase from baseline of ≥ 2 BMI-for-age/gender percentile categories		decrease from baseline of ≥ 2 BMI-for-age/gender percentile categories	
Height ⁴	increase from baseline of ≥ 2 height-for-age/gender percentile categories		decrease from baseline of ≥ 2 height-for-age/gender percentile categories	

bpm=beats per minute; CDC= Centers for Disease Controls and prevention

¹ Blood pressure percentiles are calculated for each blood BP record using the method described in Appendix B of the following reference: The Fourth Report on Diagnosis, Evaluation and Treatment of High Blood Pressure in Children and Adolescents. Pediatrics 2004; 114; 555.

² Fleming S, Thompson M, Stevens R, et al. Normal ranges of heart rate and respiratory rate in children from birth to 18 years of age: a systematic review of observational studies. Lancet 2011; 377: 1011-18.

³ BMI-for-age/gender percentiles categories (P3, P5, P10, P25, P50, P75, P85, P90, P95, P97) are obtained from the CDC Growth Charts.

⁴ Height-for-age/gender percentiles categories (P3, P5, P10, P25, P50, P75, P90, P95, P97) are obtained from the CDC Growth Charts.

The number and percentage of patients with notable vital sign values (high/low) will be presented.

Graphical presentations of vital signs (e.g., body weight, body mass index, systolic blood pressure, diastolic blood pressure) over time for change from baseline may be produced via boxplots based on time windows and corresponding tables displaying the statistics used for the box plots by the selected time points.

A listing of all vital sign assessments will be produced and notable values will be flagged. In the listing, the assessments collected outside of on-treatment period will be flagged.

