2.8.4.5 Development (Growth and sexual maturation)

Growth

Graphical displays of percentile of height and weight over time will be provided for signal detection of impact on growth development. In case of a signal, further analyses may be provided.

In addition, a shift tables for height, weight, and BMI will be provided using following low/normal/high/(low and high) classification to compare baseline to the worst on-treatment value. Low: below the 5th percentile, Normal: between 5th and 95th percentiles, High: above the 95th percentile. Percentiles are based on CDC Growth Charts, derivation is described below.

Height and BMI will be summarized at 6-month intervals, using the standard deviation scores (SDS, also called z-score), velocity and velocity SDS as appropriate. The relevant height and weight values for each 6-month period are defined using time windows, according to [Table 2-1](#). The z-scores will allow identification of potential outliers.

SDS will be calculated using the current formulae provided by the CDC as follows:

$$\text{Calculate } z_{\text{ind}} = \frac{\left(\frac{x}{M}\right)^L - 1}{LS}$$

where:

- X is height in centimeters or BMI in kilograms/m²,
- L, M and S are height or BMI-, sex- and age-specific reference values from the CDC Growth Charts.

The CDC Height-for-age and BMI-for-age L, M and S reference values for males and females are available under <https://www.cdc.gov/growthcharts>. The age category immediately above the patient's exact age should be used. SDS is actually a Z score that measures the distance from the population mean in units of standard deviations. That is, SDS < 0 refers to values lower than the population mean, and for example SDS ≤ -1.645 refers to values in the lowest 5%. The percentile can be derived from the z-score by a normal distribution.

Height velocity is defined as follows:

Height velocity (cm/6-months) = (height in time window k – height in time window $k-1$) \div ([assessment date in time window k – assessment date in time window $k-1$] \div [365.25/2]),

and similarly for weight velocity.

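### Table 2-4 cannot flag a child who starts below the 5th percentile as notably low for height or BMI, so the notable-value counts can miss further loss that the plots and listings would still show

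*SAP*

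**What the plan says.** SAP 2.8.4.2, Table 2-4, gives the criteria for notably abnormal vital signs. Height is notably low after a "decrease from baseline of ≥ 2 height-for-age/gender percentile categories". Weight is judged on BMI and is notably low after a "decrease from baseline of ≥ 2 BMI-for-age/gender percentile categories". The high criteria mirror these.

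The footnotes give the cut-points: "Height-for-age/gender percentiles categories (P3, P5, P10, P25, P50, P75, P90, P95, P97) are obtained from the CDC Growth Charts" and "BMI-for-age/gender percentiles categories (P3, P5, P10, P25, P50, P75, P85, P90, P95, P97) are obtained from the CDC Growth Charts". The SAP does not say which side of a cut-point belongs to which category. Neither row has an absolute low limit, whereas blood pressure in the same table is low at or below the 5th percentile.

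The rule feeds a table of the number and percentage of patients with notable values, and "A listing of all vital sign assessments will be produced and notable values will be flagged".

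SAP 2.8.4.5 covers growth separately. It plans percentile plots of height and weight, 6-monthly SDS and velocity summaries where appropriate, a listing of all percentiles and SDS, and a baseline-to-worst shift table for height, weight and BMI. The shift-table classes are "Low: below the 5th percentile, Normal: between 5th and 95th percentiles, High: above the 95th percentile".

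**The concern.** A rule that counts category steps needs enough categories below the starting point. At the bottom of the chart there are too few, so the children who start shortest or thinnest cannot become notable. The shift table does not help, because a child classed low at baseline can only remain low. These are the two tabulations of growth loss from baseline with fixed limits, and both miss the same children. Those children nevertheless stay in the denominator of the n (%).

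Such children are foreseeable. Exclusion criterion 14 in protocol 5.2 bars growth retardation only if it is endocrine or kidney related and precedes the diagnosis that led to transplant. Steroid-refractory subjects may enter with up to 18 months of corticosteroids (inclusion criterion 3, protocol 5.1). Protocol 4.5 discusses a possible effect of the drug on skeletal growth. A low count of notable height values could therefore be read as reassurance that it cannot fully give.

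**Working it through.** **Inputs.** Cut-points come from the footnotes to Table 2-4. The conversion is the SAP's own: "The percentile can be derived from the z-score by a normal distribution" (2.8.4.5).

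**Reproducing the plan's figure.** The SAP says "SDS ≤ -1.645 refers to values in the lowest 5"%. The inverse normal gives z(0.05) = -1.6449, which agrees.

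**Cut-points as z-scores (height).** P3 -1.881, P5 -1.645, P10 -1.282, P25 -0.674, P50 0, P75 0.674, P90 1.282, P95 1.645, P97 1.881. BMI adds P85 at 1.036.

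**Step 1: categories available below.** Nine height cut-points give ten bands and ten BMI cut-points give eleven. Below the band under P3 there are 0 bands; below P3-P5 there is 1. The rule needs 2, so it cannot be met by any child starting below P5. A fall from the 4th to the 0.01th percentile, 1.97 SD, is not flagged. Which side of a cut-point is closed matters only for a child exactly on P5. By symmetry, P95-P97 has one band above and the top band has none, so no rise from above P95 can be flagged.

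**Step 2: fall needed elsewhere.** Fall needed = z(start) minus z(upper edge of the band two below). For P5-P10, that edge is P3: at the bottom, -1.645 + 1.881 = 0.236; at the top, -1.282 + 1.881 = 0.599. For height (from unrounded z-scores):

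| Starting band | Must fall below | Bottom | Mid-percentile | Top |
|---|---|---|---|---|
| P5-P10 | P3 | 0.236 | 0.441 | 0.599 |
| P10-P25 | P5 | 0.363 | 0.710 | 0.970 |
| P25-P50 | P10 | 0.607 | 0.963 | 1.282 |
| P50-P75 | P25 | 0.674 | 0.993 | 1.349 |
| P75-P90 | P50 | 0.674 | 0.935 | 1.282 |
| P90-P95 | P75 | 0.607 | 0.765 | 0.970 |
| P95-P97 | P90 | 0.363 | 0.469 | 0.599 |

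Above P97 the fall needed starts at 0.236 and grows without limit. BMI matches height up to P75; its smallest mid-percentile value is 0.403, in P90-P95.

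- Edge to edge: 1.349 / 0.236 = 5.7-fold, height and BMI.
- Mid-band: 0.993 / 0.441 = 2.3-fold for height; 0.993 / 0.403 = 2.5-fold for BMI.

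**Step 3: how many children.** The documents give no baseline height distribution, so this is an assumption shown as a range. Take baseline height SDS as normal with SD 1 and mean m. The share below P5 is Φ(-1.645 - m).

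| Assumed mean m | Share below P5 | Of 46 enrolled |
|---|---|---|
| 0 | 0.050 | about 2 |
| -0.5 | 0.126 | about 6 |
| -1.0 | 0.259 | about 12 |
| -1.5 | 0.442 | about 20 |

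The 46 is the enrolment stated under Amendment 2 in the protocol. The Safety Set may be smaller, because the SAP moves some subjects to a listing-only set.

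**Step 4: would a flat SDS rule do as a replacement?** Take a fall of 1.0 SDS as an example. The table shows that today's rule flags every child starting between P5 and P25 after a fall of at most 0.970. A 1.0 SDS rule in its place would be stricter for all of them.

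**The case against.** The strongest reply is that Table 2-4 is a vital-signs flag and growth has its own section. In SAP 2.8.4.5 the percentile plots and the listing of percentiles and SDS are firm commitments. With 46 subjects, a child moving from SDS -1.7 to -2.7 would be seen in the listing. This stands. A reader might infer that growth loss in short children would go undetected; the documents do not support that. The reply is weaker for the SDS and velocity summaries: the SAP plans them only where appropriate, protocol 12.5.2.4 makes them depend on a signal, and neither sets a threshold for further fall.

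A reader might also take growth retardation to be the main paediatric risk. Protocol 4.5 names myelosuppression, infections, bleeding and non-melanoma skin cancer as the important risks. It raises skeletal growth separately, from juvenile-rat data, and projects the greatest effect below 2 years of age. The enrolled groups (22 + 17 + 7 = 46) include no child under 2, and 22 were 12 or older. The weight row concerns BMI change, not linear growth.

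A five-fold variation in the threshold is another tempting reading. It compares band edges, and much of it is position within a band; the mid-band spread is about half that.

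Finally, the SAP's change history says the vital-sign criteria were updated to match those used in the interim CSR. Replacing them would break that consistency, which is a good reason to add a flag and leave the rule in place.

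**Conclusion.** The gap is certain for the flag and its counts. Given the cut-points in Table 2-4, no child below P5 at baseline can be notably low for height or BMI, and none above P95 can be notably high. The shift table has the same limit. The n (%) can therefore understate loss, because its denominator includes children who cannot be counted. For starts between P5 and P97, the flag responds to falls of 0.24 to 1.35 SDS depending on exact starting percentile.

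The z-score figures rest only on the SAP's normal conversion. The share of children affected (5% to 44%) rests wholly on assumed baseline means with SD 1.

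Severity is minor. This is a descriptive safety flag in a single-arm study, no decision rule depends on it, and the plots and listing would still show the falls.

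**What to change.** Keep the category rule in Table 2-4, for consistency with the interim CSR. Beside it, add a flag for change from baseline in height SDS and BMI SDS, using the z-scores already derived in SAP 2.8.4.5. The sponsor should pre-specify the threshold, since the documents offer none. Apply the flag at least to children starting below P5 (for a fall) and above P95 (for a rise). It should supplement the present rule, because a flat threshold such as 1.0 SDS in its place would lose sensitivity between P5 and P25.

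Report how many children start below P5 or above P95, and give their SDS change separately. The shift table already has a baseline-low row; what is missing is the size of change within it.

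Cost: SAP wording, one extra derived flag and a short summary. No new data are needed. Because the flag is an addition, counts of notable values can only stay the same or rise.

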1.2 Study objectives and endpoints

Objectives and related endpoints are described in [Table 1-1](#) below.

Table 1-1 Objectives and related endpoints

Objective(s)	Endpoint(s)	Analysis	Analysis incl. in final CSR
Primary objective(s)	Endpoint(s) for primary objective(s)	Primary Analysis	

To evaluate the activity of ruxolitinib added to standard dose corticosteroids +/- CNI in pediatric subjects with moderate or severe treatment naive-cGvHD or SR-cGvHD measured by overall response rate (ORR) at Cycle 7 Day 1 based on all subjects in the study.	
Overall response rate (ORR) at Cycle 7 Day 1, defined as the proportion of subjects demonstrating a complete response (CR) or partial response (PR) without the requirement of additional systemic therapies for an earlier progression, mixed response or non-response. The response is assessed per NIH consensus criteria (Lee et al 2015), and scoring of response will be relative to the organ stage at the start of study treatment.	
Refer to Section 2.5.1	No
Secondary objective(s)	Endpoint(s) for secondary objective(s)	Secondary analysis	

To assess pharmacokinetics (PK) of ruxolitinib in treatment-	
Ruxolitinib concentrations by timepoint	
Refer to Section 2.9	No

Objective(s)	Endpoint(s)	Analysis	Analysis incl. in final CSR
naïve cGvHD and SR-cGvHD pediatric subjects			
• To evaluate the safety of ruxolitinib	• Safety and tolerability will be assessed by monitoring the frequency, duration and severity of Adverse Events, including occurrence of any second primary malignancies or infections, and by performing physical exams and evaluating changes in vital signs, tanner stage, chemistry and hematology results from baseline.	• Refer to Section 2.8	Yes
• To assess duration of response (DOR)	• Duration of response (DOR) is assessed for responders only. DOR is defined as the time from first response until cGvHD progression, death, or the date of addition of systemic therapies for cGvHD.	• Refer to Section 2.7.2	Yes
• To estimate ORR at end of Cycle 3	• Proportion of subjects who achieve OR (CR+PR) at Cycle 4 Day 1		No

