2.1.1 General definitions

Investigational treatment and study treatment

Investigational treatment, will refer to the ruxolitinib only, while *other study treatment* will refer to concomitant use of corticosteroids to treat treatment-naive cGvHD or SR-cGvHD.

Study treatment, will include both *Investigational treatment* and *other study treatment*.

Date of first administration of study treatment

The date of first administration of study treatment is derived as the first date when a nonzero dose of ruxolitinib was administered as per the DAR eCRF. The date of first administration of study treatment will also be referred as *start of study treatment*.

Date of last administration of study treatment

The date of last administration of study treatment is defined as the last date when a nonzero dose of ruxolitinib was administered as per DAR eCRF. The date of last administration of study treatment will also be referred as *end of study treatment*.

Study day

The study day, describes the day of the event or assessment date, relative to the reference start date.

The study day is defined as:

- The date of the event (visit date, onset date of an event, assessment date etc.) – reference start date + 1 if event is on or after the reference start date;
- The date of the event (visit date, onset date of an event, assessment date etc.) – reference start date if event precedes the reference start date.

The reference start date for all assessments (e.g. safety, efficacy, PK, biomarker, etc.) is the start of study treatment.

The study day will be displayed in the data listings. If an event starts before the reference start date, the study day displayed on the listing will be negative.

Time unit

A year length is defined as 365.25 days. A month length is 30.4375 days (365.25/12). If duration is reported in months, duration in days will be divided by 30.4375. If duration is reported in years, duration in days will be divided by 365.25.

Baseline

For safety and efficacy evaluations, the last available assessment on or before the date of start of study treatment is defined as “baseline” assessment.

If patients have no value as defined above, the baseline result will be missing.

On-treatment assessment/event and observation periods for safety analyses

The overall observation period will be divided into three mutually exclusive segments:

1. ***pre-treatment period***: from day of patient's informed consent to the day before first administration of ruxolitinib.

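### The notable blood-pressure count has no baseline comparison or visit structure, so it cannot separate pressure already high at entry from a rise on treatment

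*SAP*

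**What the plan says.** The safety endpoint in SAP Table 1-1 includes "evaluating changes in vital signs, tanner stage, chemistry and hematology results from baseline". For vital signs, SAP Table 2-4 calls systolic (SBP) or diastolic (DBP) pressure notably high at "≥ 95th percentile of the age and height group" and notably low at "≤ 5th percentile of the age and height group". The footnote adds: "Blood pressure percentiles are calculated for each blood BP record". On the period covered, SAP 2.8.4.2 says "Vital signs collected on treatment will be summarized". The output is then: "The number and percentage of patients with notable vital sign values (high/low) will be presented".

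Other parts of the plan do use baseline. In Table 2-4 itself, notably high weight is an "increase from baseline of ≥ 2 BMI-for-age/gender percentile categories", and height is handled in the same way. SAP 2.8.3 plans shift tables from baseline for laboratory values, and SAP 2.8.4.5 plans them for height, weight and BMI. A baseline for blood pressure is available: in SAP 2.1.1, "the last available assessment on or before the date of start of study treatment is defined as" baseline. Change-from-baseline boxplots of SBP and DBP are mentioned in SAP 2.8.4.2 but are optional.

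**The concern.** By construction, about 5% of readings in the reference population lie in each tail. A child measured many times has many chances to cross a threshold, so a count of children ever notable grows with the number of readings even if nothing happens. The trial is single-arm, so no control column shows that background rate.

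The count also ignores where the child started. Corticosteroids are required and calcineurin inhibitors are permitted (protocol 6.1), so some children may enter with raised pressure. They would be counted as notable on treatment whether or not anything changed. At stake is the reading of a safety table: a percentage well above 5% could be taken as a drug effect, or a real rise could be dismissed as background, and the table has nothing to decide between them.

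**Working it through.** The documents give no expected flag rate, so there is no plan figure to reproduce.

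**Readings per child** (protocol 8.2.1 and Table 8-1)
- Cycle 1 Days 8, 15 and 22: 3
- Cycles 2 to 7, Day 1: 6, so 9 by Cycle 7 Day 1
- Cycles 9, 12, …, 39: (39 − 9)/3 + 1 = 11
- End of treatment: 1
- Total 3 + 6 + 11 + 1 = 21. By one year (Day 309), 9 + 2 = 11.

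**Model for one cell, SBP high.** Each reading is a standard normal score, notable at 1.645 or more, so 5% per reading. With m independent readings, P(ever high) = 1 − 0.95^m. For correlated readings, score = √ρ·u + √(1−ρ)·e with u the child effect, and P(ever high) is the average over u of 1 − Φ((1.645 − √ρ·u)/√(1−ρ))^m. The within-child correlation ρ is an assumption, varied from 0.3 to 0.7.

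**No drug effect, children at the reference distribution**

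| Readings | Independent | ρ = 0.3 | ρ = 0.5 | ρ = 0.7 |
|---|---|---|---|---|
| 9 | 37% | 29% | 23% | 18% |
| 11 | 43% | 33% | 26% | 19% |
| 21 | 66% | 45% | 35% | 24% |

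If all 46 enrolled children were analysed with all 21 readings, ρ = 0.5 gives 0.347 × 46 ≈ 16 flagged SBP-high; a single visit would give 0.05 × 46 ≈ 2.

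**Can the count tell the two explanations apart?** (21 readings)

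| Scenario | ρ = 0.3 | ρ = 0.5 | ρ = 0.7 |
|---|---|---|---|
| Enter at reference mean, rise 0.5 SD on treatment | 73% | 59% | 45% |
| Enter 0.5 SD high, no change | 73% | 59% | 45% |

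The rows agree because the rule sees only on-treatment values, which have the same distribution in both scenarios.

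**What each remedy does** (21 readings)
- *Percentage notable at each visit, with a baseline row.* With a 0.5 SD shift, P(high) at one visit is 1 − Φ(1.645 − 0.5) = 12.6%. A rise on treatment shows as 5% at baseline and 12.6% afterwards; pre-existing elevation shows as 12.6% at both. This separates them.
- *Newly high only (not high at baseline).* With no effect, 21–44% are still flagged, because readings still accumulate. At ρ = 0.5 the rise gives 57% and the pre-existing elevation 54%, so this split alone hardly separates them.
- *High at two consecutive visits.* With no effect, 8–9% are flagged; about 6–7% if the child must also not be high at baseline.

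**The case against.** The strongest reply is that the count is one descriptive screen within a larger plan. Protocol 12.5.2.3 commits to vital-sign summary statistics by group and visit, and SAP section 4 does not withdraw this. SAP Table 2-1 defines visit windows that name vital signs and include a baseline row. SAP 2.1.1 allows baseline data to be summarised where appropriate. Clinically significant abnormal results are also reported as graded adverse events, and every notable reading is flagged in the listing. All of this stands, and a reader should not infer that the plan ignores baseline pressure. But summary statistics of the pressures do not say how many children were already notable before the first dose, and the boxplots are not committed.

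Three stronger readings are tempting and not supported.
- *Most children will be flagged.* This holds for a pooled any-of-four-cells figure (70–95% at 21 readings, also assuming an SBP–DBP correlation of 0.6). The SAP splits high and low and specifies no pooled row. The SBP-high cell stays below half for ρ of 0.3 to 0.7.
- *The table cannot show a drug effect.* It would move: at ρ = 0.5 and 21 readings, a 0.5 SD rise takes SBP-high from about 35% to 59%. What it cannot do is attribute the figure.
- *Age-group columns are not comparable.* They would differ if time on treatment differed, but the documents do not show that it does.

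It is also fair that a baseline comparison would not isolate ruxolitinib, because corticosteroids are tapered in responders and there is no control arm. It would still remove pre-existing elevation as an explanation.

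**Conclusion.** The concern holds in a limited form. The notable-value table for SBP and DBP has no baseline comparator and no visit structure, which is at odds with the stated endpoint and with how the same plan treats weight, height and laboratory values. With no drug effect, about 24–45% of fully followed children would appear as SBP-high, or about 18–29% with 9 readings, and the figure cannot distinguish entry level from on-treatment change.

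This rests on four assumptions: that the count means notable at any on-treatment reading, which is the natural reading but not the SAP's wording; ρ between 0.3 and 0.7; reference-population pressures at entry; and full attendance. Early discontinuation lowers the rates, since 21 is a maximum. The issue concerns safety reporting and does not touch the primary endpoint.

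**What to change.** Keep the existing count and the flagged listing, and amend SAP 2.8.4.2 as follows.
1. Add the number and percentage notable, high and low, for SBP and DBP at baseline and at each Table 2-1 window. This is the part that separates the two explanations. With 46 children the visit figures will be imprecise (5% is about 2 children, 12.6% about 6), so they should be read as a pattern across visits.
2. Report children not notable at baseline separately from those already notable, for example as a shift table by baseline category. A baseline-to-worst shift table should not stand alone, because it still accumulates over visits.
3. Make the by-visit and change-from-baseline blood-pressure summaries firm commitments.
4. State in words how the count treats repeated readings.

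A count of children not notable at baseline and then notable at two consecutive visits may be added as a supplementary row. It should not replace the existing count: it drops isolated readings, and from Cycle 9 confirmation takes about 12 weeks.

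The cost is SAP wording and one or two extra tables from data already collected, with no change to trial conduct.
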